6.1 Clinical investigation flow chart

6.1.1 Cohort A (Prospective)

All the patients enrolled prospectively will follow the below clinical investigation flow. This group of patients is in Cohort A.

Figure 4: Clinical investigation flow chart (Cohort A-prospective)

[figure not shown]

6.1.2 Cohort B

All the patients, who participated in a SJM sponsored regulatory or first-in-human trial and who consented to participate in this extended follow-up clinical investigation will follow the below clinical investigation flow. This group of patients will constitute Cohort B.

- For these patients, the data collection will start after consent is obtained and will include any study related event (AE, unscheduled visit, etc.) documented after the patient has exited the SJM sponsored regulatory or first-in-human trial.
- For these patients, the data collected up to the 1 year follow-up visit will not need to be re-collected.

Figure 5: Clinical investigation flow chart (Cohort B)

6.2 Clinical investigation activities and visits

Table 2 : List of clinical investigation activities and visits

Study activities and visits	En/Bas*	Imp*	P-Dis*	30 d*	1 Y*	2 Y	3 Y	4 Y	5 Y
Visit window	-6m-0**	0	0-7d	-7d+14d	±90d	±90d	±90d	±90d	±90d
Informed Consent	X								
Patient's eligibility assessment	X								
Angiography	X								
Demographics	X								
Medical and Cardiovascular History	X								
Native aortic valve assessment	X								
Access site assessment	X								
Surgical risk assessment	X								
Frailty assessment:									
- 5 meters walking time	X			X	X				
- Grip strength	X			X	X				
- Wasting and malnutrition parameters	X			X	X				
- Cognitive impairment or dementia (MMSE)	X			X	X				
Blood sample:									
- Serum Albumin (Frailty assessment)	X			X	X				
- Hemoglobin, Creatinine (if available)	X		X	X	X				
- Troponin	X		X ^a	X	X				
Physical assessment	X		X	X	X	X	X	X	X
12 lead ECG	X		X ^b	X	X				
Paced rhythm assessment ^f				(X)					
Medication assessment	X	X	X	X	X	X	X	X	X

Clinical Investigation Plan – PORTICO I

Echocardiography	X	X ^c	X	X	X	X	X	X	X
NYHA Classification	X		X	X	X	X	X	X	X
QoL questionnaire (EQ-5D)	X ^d		X	X	X				
The six-minute walking test	X			X	X	X	X	X	X
Modified Rankin Scale ^e	X		X	X	X				
Adverse Events Assessment	X	X	X	X	X	X	X	X	X
Device Deficiency Assessment	X	X	X	X	X	X	X	X	X
Resources utilization		X	X						

(X) as applicable

* For Cohort B, the informed consent and eligibility assessment will be conducted but all the other above mentioned data up to 1 year will not be re-collected (equivalent to grey background). Depending on time point of informed consent signed, the patient will enter the Portico I study at 1Y or later.

** For Cohort A, tests to confirm baseline measurements (e.g. Angio, CT, echocardiogram) should be within 6 months of index procedure.

^a Blood Sample for Troponin to be obtained between day 2 and 4 post-implant or at discharge whatever occurs first.

^b ECG within 24 hrs Post-implant AND at discharge but no later than 7 days Post-implant-whatever occurs first.

^c Assess aortic regurgitation with TEE if available or via fluoroscopy/angiography

^d The QoL questionnaire should be completed by the patient the closest possible to the implant date

^e The Modified Rankin scale should be completed additionally (if possible) 90 days after any neurological event (stroke, TIA, encephalopathy).

^f The permanent paced rhythm assessment is performed only if applicable

Table 3: Clinical investigation activity definition

Study activities	Definitions
Informed Consent	An Ethics Committee (EC) and Sponsor approved Informed Consent must be obtained in accordance to section 7.2 (Informed Consent Process) of this Clinical Investigation Plan.
Patient’s eligibility assessment	Refer to the patient’s eligibility assessment process as illustrated in Figure 3 .
Demographics (NAP for Cohort B)	Patient’s Age and Gender
Medical and Cardiovascular History (NAP for Cohort B)	
Medical and Cardiovascular history of the patient:
 
 • Cardiovascular and neurovascular history • Previous cardiovascular procedures • Other medical conditions (e.g., diabetes, kidney disease, lung disease, etc.) • Baseline status and risk factors
Native aortic valve assessment (NAP for Cohort B)	
Native aortic valve information such as annulus size or valve morphology will be collected based on examinations conducted at the investigational site as standard of care. We recommend the use of Multi Slice Computed Tomography (MSCT) in particular for annulus sizing; however other imaging modalities, such as Trans Esophageal Echocardiography (TEE) are also acceptable.
 
It is recommended to perform both non-contrast and contrast MSCT, if routinely performed. It is also recommended to perform both thoracic and abdominal CT, if routinely performed.
 
MSCT exams (if routinely performed) and any other data acquired as part of patient’s native aortic valve assessment (such as additional (pre-) sizing information), should be sent to Sponsor on request only. If requested, MSCT should be recorded in Dicom format and all material should be de-identified and sent to the sponsor.

Access site assessment (NAP for Cohort B)	Patient’s recommended TAVI access site characteristics (Transfemoral, transapical, etc.)
Surgical Risk Assessment (NAP for Cohort B)	Three Surgical Risk Assessment tools will be used: Logistic EuroSCORE I, Logistic EuroSCORE II and the STS Risk Score. Refer to Appendix E: Surgical Risk Assessment Tools, for links to the on-line score calculators.
Frailty assessment (NAP for Cohort B)	
Patient Frailty index will be assessed at baseline, at 30 days and at 1 Year. Frailty is a risk factor not included in the current surgical risk assessment tools. Frailty Index assessment will include:
 
 - 5 meters walking time - Grip strength - Wasting and malnutrition parameters (including weight loss, BMI and Serum albumin value to be obtained via blood sample)

Study activities	Definitions
	
- Cognitive impairment or dementia as measured with the mini-mental state examination (MMSE).
 
For further details/instructions, please refer to Appendix F: Frailty Assessment.

Blood sample (NAP for Cohort B)
	
 • Albumin: see frailty assessment • Hemoglobin, Creatinine (if available) • Troponin: at Enrollment/Baseline and between day 2 and 4 Post-implant or at discharge whatever occurs first.

Physical assessment (From 2Y visit onward for Cohort B)
	
At the baseline visit the following measurement must be assessed:
 
 • Height • Weight • Systolic/Diastolic blood pressure 
The following measurements must be assessed at all visits:
 
 • Weight • Systolic/Diastolic blood pressure

12 Leads ECG (NAP for Cohort B)
	
Assessment of dominant rhythm, heart rate, PR interval, QRS duration, bundle branch block, fascicular block etc.
 
The ECG is to be performed at baseline, within 24 hours Post-implant, at hospital discharge but no later than 7 days Post-implant, whatever occurs first and at 30days and 1 Year.

Medication assessment (From 2Y visit onward for Cohort B)
	
The following information on medication will be collected at each visit:
 
 • Beta Blockers • Calcium Channel Blockers • Anticoagulants • Antiplatelet agents including Aspirin • Diuretics • Ace-Inhibitors • Angiotensin Receptor Blocker (ARBs) • Statins 
At the implant visit the prophylactic antibiotics regimen will also be collected

Echocardiogram (From 2Y visit onward for Cohort B)
	
Each site will be responsible for performing and interpreting the baseline & post-implant and follow-up echocardiograms using the VARC 2 definitions.
 
For further details on echocardiographic variables, please refer to Appendix D: VARC 2 Endpoints Definitions.

Study activities	Definitions
	
Echocardiograms can be requested to be sent to an echo Core Laboratory. If requested, exams should be recorded in Dicom format and should be de-identified prior to sending. Routine echocardiograms can be used to complete the echocardiogram study Case Report Forms (CRFs).

NYHA Classification (From 2Y visit onward for Cohort B)
	
The New York Heart Association (NYHA) Functional Classification provides a simple way of classifying the extent of heart failure.

QoL questionnaire (EQ-5D) (NAP for Cohort B)
	
The EQ-5D questionnaire will be used. It is a standardized instrument for use as a measure of health outcomes.

The six-minute walking test (From 2Y visit onward for Cohort B)
	
The six-minute walking test (6MWT) is a commonly used objective measure of functional exercise capacity in individuals with moderately severe impairment. For further details/instructions, please refer to Appendix G: ATS Guidelines²⁵ for the Six Minute Walk Test instructions.

Modified Rankin scale (mRS)
	
The modified Rankin Scale (mRS) is a functional measurement to assess the degree of disability or dependence in the daily activities of people who have suffered a stroke. mRS at Enrollment/Baseline, 30days, 1year and is to be completed additionally (if possible) 90days after any neurological event (stroke, TIA, encephalopathy) This assessment must be completed by a rater who has a current certificate that demonstrates completion of an accredited training program for this stroke scale, using the structured interview found in Appendix H: Structured Interview for the Modified Rankin Scale (mRS).


Portico Valve Implant (NAP for Cohort B)
	
Procedural information must be collected including:
 
 • Pre-implant information (such as access type, use of balloon valvuloplasty, etc.) • Implant information (such as prosthetic valve information, use of rapid pacing, etc.) • Aortic regurgitation • Implant depth and prosthesis-patient mismatch • Post-implant information including hemodynamics 
The assessment of aortic regurgitation must be performed with a combination of echocardiography, angiography and hemodynamic approach, preferably according to the instructions provided in Appendix I: Peri-procedural instructions.
 
Implant depth measurement should be assessed via aortic root angiography and further instructions are also provided in Appendix I: Peri-procedural instructions.
 
Prosthesis-patient mismatch will be measured by means of echocardiography according to the VARC 2 guidelines.

Study activities	Definitions
	Any other data acquired as part of the patient's implant procedure (such as routinely performed aortography) can be collected by the Sponsor as well to obtain additional procedural information regarding the implant.
Adverse Events Assessment (From 1Y visit onward for Cohort B)	All adverse events will be documented according to Section 7.3 (Adverse Events, Adverse Device Effect, and Device Deficiency).
Device Deficiency Assessment	All device deficiencies will be documented according to Section 7.3 (Adverse Events, Adverse Device Effect, and Device Deficiency).
Paced Rhythm Assessment (NAP for Cohort B)	If the patient received a new permanent pacemaker, due to an AV-block, within 30 days after their TAVI procedure, then the patient's dependence to pacemaker will be checked according to the recommendations provided in Appendix J: Recommendation for paced rhythm assessment in patients with a TAVI related implantation of permanent pacemaker.
Resource utilization Assessment (until discharge for COHORT A) (NAP for Cohort B)	Procedural resources: Material resources such as devices used during the procedure (valve, guiding catheters, valvuloplasty balloons, etc.), operators' resources and procedure duration will be collected at procedure time. Hospital resources: length of stay in different wards (ICU, non ICU, etc.); will be collected at discharge.

Table 4: Data Collection Forms for COHORT A and COHORT B (identical to Cohort A with exception of grey background boxes)

Study activities		En/Bas	Imp	P-Dis	30 d	1 Y	2 Y	3 Y	4 Y	5 Y
Enrollment Form		X								
Baseline Form		X								
Portico Valve Implant Form			X							
Echocardiogram Form		X		X	X	X	X	X	X	X
EQ-5D Form		X		X	X	X				
Follow-Up Visit Form				X	X	X	X	X	X	X
Adverse Events Form		(X)	(X)	(X)	(X)	(X)	(X)	(X)	(X)	(X)
Device Deficiency Form		(X)	(X)	(X)	(X)	(X)	(X)	(X)	(X)	(X)
Deviation Form		(X)	(X)	(X)	(X)	(X)	(X)	(X)	(X)	(X)
Termination Form		(X)	(X)	(X)	(X)	(X)	(X)	(X)	(X)	X
Death Form		(X)	(X)	(X)	(X)	(X)	(X)	(X)	(X)	(X)
Exams	All exams (ECG, Echo, angio, MSCT and any other exam) should be provided to Sponsor on request. In addition, Echocardiograms can be requested to be sent to an echo core laboratory. If requested, exams should be recorded in Dicom format and should be de-identified prior to sending.									

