5.3.2 Secondary Endpoints

- Evaluation of the VARC-2¹⁹ defined event rates at 30 days, 1 year and annually through 5 years post implant. Definitions are detailed in Appendix D: VARC 2 Endpoints Definitions.
 - All-Cause Mortality
 - Cardiovascular Mortality
 - Myocardial Infarction
 - Stroke (disabling and non-disabling)
 - New or worsened conduction disturbances and cardiac arrhythmias (including pacemaker implantation rate at 30 days and new-onset atrial fibrillation (AF))
- Evaluation of the VARC-2¹⁹ defined event rates at 30 days from the index procedure.
 - Vascular access site complication (major and minor)
 - Bleeding (life-threatening, major and minor)
 - Acute kidney injury

- Prosthetic valve function at 30 days, 1 year and annually through 5 years post implant. (Includes prosthetic valve stenosis and prosthetic valve regurgitation).
- Clinical benefit endpoints at 30 days, 1 year and annually through 5 years post implant (if available)
 - NYHA functional classification
 - 6 Minute Walk Test (6MWT)
 - Quality of life measured with EQ-5D questionnaire through 1 year post-implant
- Evaluation of the TAVI-related resource utilization through hospital discharge (e.g. index procedural hospital/physician resources)
- Interim reporting at 30 days and 1-year all-cause mortality data may be performed on a subset of patients and compared with an appropriate external comparator. The results will be presented to appropriate agencies in France and in other countries where it will be deemed necessary for reimbursement purposes.

NOTE: Should new VARC or ESC Guidelines be published, endpoint analysis would be adjusted accordingly and analyzed to the extent that the previously gathered data supports the analyses based on the most current guidelines.

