6.2.2. Baseline Visit (Cohort A only)

This visit can take place the same day as the enrollment visit. The data from previously conducted diagnostic tests/procedures, as indicated with an “ (X) as applicable

, performed as standard of care will be collected during this visit. It is not necessary to repeat these tests if they were collected within the clinical investigation visit window. All other data must be collected after obtaining clinical investigation specific consent and within 45 days prior to the TAVI procedure. The baseline visit consists of the following activities:

- Demographics
- Medical and Cardiovascular History
- Native aortic valve assessment
- Access site assessment (Trans-femoral, trans-apical, etc.)
- Surgical Risk Assessment
- Frailty Assessment (including assessment of 5 meters walking time, grip strength, wasting and malnutrition and cognitive impairment or dementia via MMSE)
- Blood sample (Serum Albumin value as part of frailty assessment. Creatinine, Hemoglobin if available (SOC) and Troponin values)
- Physical Assessment
- 12 lead ECG
- Medication assessment
- Echocardiogram
- NYHA Classification
- QoL questionnaire (EQ-5D)
- 6MWT
- Modified Rankin Scale
- Adverse events assessment
- Device Deficiency assessment

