6.2.4. Pre-Discharge visit (Cohort A only)

The pre-discharge visit will take place at the time of hospital discharge or within seven days after the index procedure, whichever occurs first. If the patient is expected to be discharged over the weekend, the discharge tests may be completed on the last week day prior to discharge. The assessment will include:

- Physical assessment
- Blood sample (between day 2 to 4 Post-implant or at discharge whatever occurs first) to obtain Hemoglobin, Creatinine and Troponin values
- 12 lead ECG (within 24hrs Post-implant and at hospital discharge but no later than 7 days Post-implant, whatever occurs first).
- Medication assessment
- Echocardiography (if a post-procedure echo has been done within 24 hours prior to discharge, an additional discharge echo is not required)
- NYHA functional classification
- QoL questionnaire (EQ-5D)
- Modified Rankin Scale
- Adverse events assessment
- Device Deficiency assessment
- Resource utilization assessment

6.2.5. 30 Day follow-up visit (Cohort A only)

The 30 Day visit will take place at 30days (-7 days, +14days) after the index procedure, and will include:

- Frailty Assessment by means of the following components: 5 meters walking time, grip strength, wasting and malnutrition (including blood sample to obtain Serum Albumin value) and cognitive impairment or dementia (via MMSE)
- Physical assessment
- 12 lead ECG
- Medication assessment
- Echocardiography
- NYHA functional classification
- QoL questionnaire (EQ-5D)

- 6MWT
- Modified Rankin Scale
- Adverse events assessment
- Device Deficiency assessment
- Permanent Pacemaker Control (if applicable)
- Resource utilization assessment

6.2.6. 1 Year follow-up visit (Cohort A only)

The 1 Year visit will take place at 365 days (\pm 90days) after the index procedure, and will include:

- Frailty Assessment by means of the following components: 5 meters walking time, grip strength, wasting and malnutrition (including blood sample to obtain Serum Albumin value) and cognitive impairment or dementia (via MMSE)
- Physical assessment
- 12 lead ECG
- Medication assessment
- Echocardiography
- NYHA functional classification
- QoL questionnaire (EQ-5D)
- 6MWT
- Modified Rankin Scale
- Adverse events assessment
- Device Deficiency assessment
- Resource utilization assessment

6.2.7. 2 Year follow-up visit

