
Bleeding (VARC 2)
	
Life-threatening or disabling bleeding
 
 • Fatal bleeding (BARC(22) type 5) OR • Bleeding in a critical organ, such as intracranial, intraspinal, intraocular, or pericardial necessitating pericardiocentesis, or intramuscular with compartment syndrome (BARC type 3b and 3c) OR • Bleeding causing hypovolemic shock or severe hypotension requiring vasopressors or surgery (BARC type 3b) OR • Overt source of bleeding with drop in hemoglobin ≥ 5 g/dl or whole blood or packed red blood cells (RBCs) transfusion ≥ 4 Units^a (BARC type 3b). 
^aGiven 1 U of packed RBC typically will raise blood hemoglobin concentration by 1 g/dl, an estimated decrease in hemoglobin will be calculated.
 
Major bleeding (BARC type 3a)
 
 • Overt bleeding either associated with a drop in the hemoglobin level of at least

	
3.0 g/dl or requiring transfusion of two or three units of whole blood/ RBC, or causing hospitalization or permanent injury, or requiring surgery AND
 
 Does not meet criteria of life-threatening or disabling bleeding 
Minor bleeding (BARC type 2 or 3a, depending on the severity)
 
 Any bleeding worthy of clinical mention (e.g., access site hematoma) that does not qualify as life-threatening, disabling or major.

Acute Kidney Injury AKIN classification (VARC 2)
	
Stage 1 Increase in serum creatinine to 150% - 199% (1.5 to 1.99 X increase compared with baseline) OR increase of ≥ 0.3 mg/dl (≥ 26.4 mmol/l) OR Urine output <0.5 mL/kg/h for >6h but <12h
 
Stage 2 Increase in serum creatinine to 200% -299% (2.0 to 2.99 X increase compared with baseline) OR Urine output <0.5 mL/kg/h for >12h but <24h
 
Stage 3 Increase in serum e to $\geq 300\%$ (> 3 X increase compared with baseline) or serum creatinine of ≥ 4.0 mg/dl (≥ 354 mmol/l) with an acute increase of at least 0.5 mg/dl (44 mmol/l) OR Urine output <0.3 mL/kg/h for ≥ 24h OR Anuria for ≥ 12h
 
Patients receiving renal replacement therapy are considered to meet Stage 3 criteria irrespective of other criteria.

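### Creatinine and hemoglobin are optional in some sections and required in others, so 30-day acute kidney injury can be under-reported

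*Combined protocol and SAP*

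**What the plan says.** **Endpoints.** Section 5.3.2 names "Bleeding (life-threatening, major and minor" and "Acute kidney injury" among the events to be evaluated at 30 days from the index procedure. Both use the Appendix D definitions.

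**Collection.** The sections differ:
- Table 2 (section 6.2) ticks "Hemoglobin, Creatinine (if available" at baseline, pre-discharge, 30 days and 1 year. The albumin and troponin rows carry no such qualifier. Table 3 repeats the qualifier.
- Section 6.2.2 (baseline) asks for "Creatinine, Hemoglobin if available (SOC) and Troponin values".
- Section 6.2.4 (pre-discharge) calls for blood at day 2 to 4 or at discharge "to obtain Hemoglobin, Creatinine and Troponin values", with no qualifier.
- Section 6.2.5 (30 days) mentions blood only for albumin, although Table 2 ticks hemoglobin and creatinine at that visit.

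**Definitions.** AKI Stage 1 in Appendix D begins "Increase in serum creatinine to 150% - 199% (1.5 to 1.99 X increase compared with baseline". Urine output is an alternative, for example "Urine output <0.5 mL/kg/h for >6h but <12h". Dialysis is covered separately: "Patients receiving renal replacement therapy are considered to meet Stage 3 criteria irrespective of other criteria".

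**Analysis.** Section 9.4 estimates all safety secondary endpoints by non-parametric survival methods and censors patients without the event at their last documented contact. It does not say what happens when the values needed to classify an event are missing.

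**The concern.** An endpoint defined by a laboratory change can be observed only in patients who have both values. If collection follows local practice and the analysis treats everyone without a recorded event as event-free, the AKI rate depends partly on how many patients were tested.

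That matters more here than in a randomized trial. The study has no concurrent or matched control, so the absolute rate is itself the result and under-ascertainment cannot cancel between arms. With about 65 centers in about 15 countries, completeness could also vary by site. Section 7.1.1 defines a deviation as a failure to meet a CIP requirement, so a missing value that was needed only where available may not be logged as one.

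**Working it through.** The protocol gives no AKI rate, bleeding rate or laboratory completeness, so there is no stated figure to reproduce. The check has two parts.

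**1. Can a patient without paired creatinine be classified?**

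Every creatinine criterion in Appendix D is a rise: a ratio to baseline, an increase of at least 0.3 mg/dl, or a level of at least 4.0 mg/dl with an acute increase of at least 0.5 mg/dl. A single discharge value meets none of them, so 6.2.4 alone does not cure an absent baseline. The other routes are:
- Urine output: a valid criterion, but not in the Table 2 schedule.
- Renal replacement: needs no creatinine, but identifies only Stage 3.
- Adverse event reporting: section 7.3.2 requires all serious events and all device effects, but limits other non-serious events to cardiovascular and neurovascular ones. A mild AKI that is not a device effect need not be reported.

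Under 9.4, an untested patient with no recorded AKI is then censored at last contact and counts as at risk and event-free until that date.

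Bleeding is different. The hemoglobin drops (3.0 g/dl for major, 5 g/dl for life-threatening) apply only to overt bleeding. Transfusion, surgery and shock are among the alternatives. A clinically notable bleed that misses the higher grades is still minor bleeding, which has no hemoglobin threshold. A missing value can lower the grade but does not remove the bleed.

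**2. How large could the AKI effect be?**

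Let p be the true rate, m the share without paired values, and q the share of events in untested patients found by another criterion. Assume testing is independent of the event. All three inputs are assumptions.

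Reported rate = p × [(1 − m) + m × q]

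| p | m | q = 0 | q = 0.5 |
|---|---|---|---|
| 15% | 10% | 15 × 0.90 = 13.5% | 15 × (0.90 + 0.05) = 14.25% |
| 15% | 20% | 15 × 0.80 = 12.0% | 15 × (0.80 + 0.10) = 13.5% |
| 15% | 30% | 15 × 0.70 = 10.5% | 15 × (0.70 + 0.15) = 12.75% |

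To compare this with sampling error, take the 866 patients of section 9.2.1 as an illustrative denominator and a Wald 95% interval, with q = 0. At m = 10% the interval is 11.2% to 15.8%, which still covers 15%. At m = 20% it is 9.8% to 14.2%, and at m = 30% it is 8.5% to 12.5%; neither covers 15%.

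**Why two denominators are needed.** Suppose evaluable means having paired creatinine or meeting another criterion. The evaluable share is (1 − m) + m × p × q. With p = 15%, m = 20% and q = 0.5 this is 0.80 + 0.20 × 0.15 × 0.5 = 0.815. The evaluable-patient rate is 13.5 / 0.815 = 16.6%, against 13.5% among all implanted patients. In this example the two rates lie on either side of the true 15%.

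**The case against.** The strongest reply is that optional collection is a deliberate choice. Section 1.1 says the revision aligns assessments with current practice, and 6.2.2 marks the baseline values as standard of care. These are descriptive secondary endpoints, and the sample size rests on 1-year mortality, which is unaffected. The post-implant sample is already listed without qualification in 6.2.4. Section 9.4 defers other secondary analyses to a separate statistical analysis plan, and adjudication follows a CEC charter. Neither is part of the document reviewed, and either might contain a missing-data rule.

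Most of this is fair and limits the weight of the point. It does not settle it: the sections still disagree, a later rule cannot supply a creatinine that was never measured, and 9.4 itself already sets the method for safety endpoints.

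Four stronger readings are tempting, and the protocol does not support them:
- *AKI and bleeding cannot be graded without these tests.* Appendix D gives other routes for both. The statement is nearly true for AKI short of renal replacement, but not for bleeding.
- *Untested bleeds vanish.* They remain at least minor bleeds if clinically notable.
- *The plan declares untested patients event-free.* This is inferred from the censoring rule and the absence of any other rule.
- *Requiring troponin but not creatinine shows misplaced priorities.* Troponin is a named biomarker in the myocardial infarction definition, and infarction is itself a secondary endpoint.

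**Conclusion.** The concern holds, mainly for AKI. The collection rules contradict each other. As written, 9.4 would leave a patient without paired creatinine in the risk set as event-free, so the 30-day AKI rate can be understated. For bleeding, the most that follows is that some overt major or life-threatening bleeds may be recorded as minor.

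The size cannot be known from the protocol. With an assumed true AKI rate of 15% and 10% to 30% of patients lacking paired values, the reported rate would be 13.5% to 10.5% if no untested event is otherwise found, and 14.25% to 12.75% if half are. These figures also assume that testing is unrelated to the event. If clinicians test mainly on suspicion, the shortfall is smaller, and a rate among tested patients alone would be too high. The primary endpoint and sample size are not affected.

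**What to change.** 1. Remove the qualifier for creatinine and hemoglobin at baseline and pre-discharge in Tables 2 and 3 and in 6.2.2, so that they agree with 6.2.4.
2. Reconcile the 30-day list in 6.2.5 with Table 2.
3. In 9.4, count AKI met by any Appendix D criterion. Restricting the analysis to patients with paired creatinine would discard events met by urine output or renal replacement.
4. Classify patients with neither paired creatinine nor another qualifying criterion as not evaluable rather than event-free. Report their number, including deaths before the post-procedure sample.
5. Show the AKI rate both among evaluable patients and among all implanted patients.

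The cost is two routine assays on blood that Table 2 already schedules (albumin and troponin at baseline, troponin pre-discharge), a few lines of text, and possibly a less favourable AKI rate. No change to the sample size is needed. This is a cheap improvement.

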Myocardial Infarction (VARC 2)	
Peri-procedural MI (≤ 72 h after the index procedure) New ischemic symptoms (e.g., chest pain or shortness of breath), or new ischemic signs (e.g. ventricular arrhythmias, new or worsening heart failure, new ST-segment changes, hemodynamic instability, new pathological Q-waves in at least two contiguous leads, imaging evidence of new loss of viable myocardium or new wall motion abnormality), Elevated cardiac biomarkers (preferably CK-MB) within 72 h after the index procedure AND consisting of at least one sample post-procedure with a peak value exceeding 15× as the upper reference limit for troponin or 5× for CK-MB. If cardiac biomarkers are increased at baseline (>99th percentile), a further increase in at least 50% post-procedure is required AND the peak value must exceed the previously stated limit.
 
Spontaneous MI (>72 h after the index procedure) Any one of the following criteria:
 
 • Detection of rise and/or fall of cardiac biomarkers (preferably troponin) with at least one value above the 99th percentile URL, together with evidence of myocardial ischemia with at least one of the following: 
 ○ Symptoms of ischemia ○ ECG changes indicative of new ischemia [new ST-T changes or new Left Bundle Branch Block (LBBB)] ○ New pathological Q waves in at least two contiguous leads ○ Imaging evidence of new loss of viable myocardium or new wall motion abnormality • Sudden, unexpected cardiac death, involving cardiac arrest, often with symptoms suggestive of myocardial ischemia, and accompanied by presumably new ST-segment elevation, or new LBBB, and/or evidence of fresh thrombus by coronary angiography and/ or at autopsy, but death occurring before blood samples could be obtained, or at a time before the appearance of cardiac biomarkers in the blood. • Pathological findings of an acute myocardial infarction.

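### The scheduled post-implant troponin may be drawn up to day 4, but the peri-procedural MI definition accepts biomarker evidence only within 72 hours, so a compliant sample can be unusable for that endpoint

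*Combined protocol and SAP*

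**What the plan says.** Three places in the protocol set the post-implant troponin sample, and they agree with one another.

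- Section 6.2, Table 2, footnote a: "Blood Sample for Troponin to be obtained between day 2 and 4 post-implant or at discharge whatever occurs first".
- Section 6.2, Table 3, blood sample row: "Troponin: at Enrollment/Baseline and between day 2 and 4 Post-implant or at discharge whatever occurs first".
- Section 6.2.4, pre-discharge visit: "Blood sample (between day 2 to 4 Post-implant or at discharge whatever occurs first) to obtain Hemoglobin, Creatinine and Troponin values".

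Table 2 gives the implant visit a window of 0. It also marks troponin at 30 days and 1 year. CK-MB is not scheduled at any visit.

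Appendix D dates the early category as "Peri-procedural MI (≤ 72 h after the index procedure". Besides new ischemic symptoms or signs, it sets a time limit on the laboratory evidence: "Elevated cardiac biomarkers (preferably CK-MB) within 72 h after the index procedure AND consisting of at least one sample post-procedure". The level that such a sample has to reach is also fixed: "with a peak value exceeding 15× as the upper reference limit for troponin or 5× for CK-MB". If the baseline value is already raised, "a further increase in at least 50% post-procedure is required AND the peak value must exceed the previously stated limit".

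For spontaneous MI, dated after 72 hours, the biomarker route in Appendix D needs three things: a rise and/or fall, at least one value above the 99th percentile URL (upper reference limit), and evidence of ischemia. New ST-T changes and new left bundle branch block are listed among the ECG changes that can supply that evidence.

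Section 5.3.2 lists MI as a secondary endpoint at 30 days, 1 year and annually through 5 years. Section 9.4 analyses safety endpoints as time to first occurrence.

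**The concern.** The sampling schedule and the endpoint definition use different clocks. A site can follow Table 2 exactly, draw the sample on day 4, and hold a value that the peri-procedural definition cannot use. No other scheduled sample fills the gap, because the next troponin is at 30 days. The protocol allows clinically driven sampling but does not require it when ischemia is suspected in the first 72 hours.

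The main consequence is a possible missed event. A patient with ischemic signs before 72 hours whose only troponin comes later may meet neither definition: the biomarker evidence is too late for the first, and the event is too early for the second.

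Patients discharged before 72 hours have an on-time sample by design, so any loss falls wholly on those with longer stays. Because section 9.4 counts time to first event, an early MI that is missed or wrongly counted carries into every later cumulative estimate.

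**Working it through.** The plan states no figure on this point to reproduce. The check sets the sampling window against the 72-hour limit and then compares the two biomarker limits.

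**Inputs.** Window of day 2 to day 4 (Table 2 footnote a, Table 3, 6.2.4); implant visit at 0 (Table 2); limit of 72 h and peri-procedural troponin limit of 15 times the upper reference limit (Appendix D); spontaneous limit of 1 times the 99th percentile URL (Appendix D). Assumption: where days are read as calendar days, the procedure takes place between 08:00 and 17:00. The documents give no clock time.

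**Share of the window beyond 72 h**

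1. Elapsed hours, implant as time 0. The window runs from 2 × 24 = 48 h to 4 × 24 = 96 h. Share beyond = (96 − 72) / (96 − 48) = 24/48 = 50%.
2. Calendar days, implant as day 0, procedure at clock hour t. The window runs from 48 − t to 120 − t, which is 72 h long. Share beyond = (120 − t − 72) / 72 = (48 − t) / 72.
3. Calendar days, implant as day 1. The window runs from 24 − t to 96 − t. Share beyond = (24 − t) / 72.

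| Procedure at | Implant = day 0 | Implant = day 1 |
|---|---|---|
| 08:00 | 40/72 = 56% | 16/72 = 22% |
| 12:00 | 36/72 = 50% | 12/72 = 17% |
| 17:00 | 31/72 = 43% | 7/72 = 10% |

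These are shares of the permitted time, not of patients. The documents do not say when within the window sites draw the sample or how many patients leave before 72 h.

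**Ratio of the two biomarker limits.** In multiples of the URL, and assuming that both definitions use the same URL, the peri-procedural limit is the larger of 15 and, for a raised baseline, 1.5 × baseline. The spontaneous limit is 1.

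- Baseline up to 10 × URL: 1.5 × 10 = 15, so the ratio is 15/1 = 15.
- Baseline 12 × URL: 1.5 × 12 = 18. Baseline 20 × URL: 1.5 × 20 = 30.
- If the 99th percentile is k times the other reference limit, the ratio is 15/k: 12 for k = 1.25, 10 for k = 1.5, 7.5 for k = 2. Appendix D words the two limits differently, so k = 1 is an assumption.

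**Whether a late routine sample could contribute to a spontaneous MI.** The scheduled baseline troponin and a raised day-4 value together can literally supply a rise. Section 4 names conduction disturbance as a known risk of the procedure, and the ECGs in Table 2 record it. If a new left bundle branch block or ST-T change is read as ischemic and dated after 72 h, the schedule itself can provide every element. Each of those conditions has to hold.

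**The case against.** **A routine troponin never makes the diagnosis alone.** Peri-procedural MI also needs ischemic symptoms or signs, and such a patient may well be sampled sooner. Any sample within 72 h counts, as does CK-MB, which the definition prefers. Serious events and cardiovascular events are reportable under section 7.3.2, and an independent committee adjudicates specified events to VARC-2 under section 14.3.2. Its charter is a separate document and may deal with late samples. This stands as a limit on how often an MI would be missed. It does not remove the conflict, because nothing in the documents shown requires an earlier sample or says how a late one is handled.

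**A reader might infer that a sample drawn after 72 h simply switches to a limit at least 15 times lower.** The documents do not support that. The 72-hour headings date the infarction, not the blood draw. Spontaneous MI also needs a rise and/or fall and evidence of ischemia, and the ECG item is confined to changes that indicate new ischemia. The ECG within 24 h of implant (Table 2 footnote b) can date an early conduction change to before 72 h. The factor of 15 holds only if both limits use the same URL.

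**Moving an MI between the two categories leaves the listed endpoint unchanged.** Section 5.3.2 lists MI without the split. This stands: only a wholly missed or wholly false MI alters the reported rate, and the documents allow neither to be estimated.

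**Another way of counting days could close the gap.** If the moment of implant were day 1 and days were counted in whole 24-hour steps, the window would end at (4 − 1) × 24 = 72 h. Table 2 puts implant at 0, so the documents do not favor that reading. That the answer turns on the convention is itself a reason to state the window in hours.

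**Conclusion.** The conflict is real. All three sampling passages permit the only troponin scheduled between implant and the 30-day visit to be drawn after the point at which Appendix D stops accepting biomarker evidence for peri-procedural MI.

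With implant as day 0, as Table 2 indicates, the unusable part is roughly the last half of the window. On a calendar-day count from day 1 it is a tenth to about a fifth. A reader might take the 50% as the share of patients affected. It is not: that share is unknown, and it is confined to patients still in hospital after 72 h.

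The direct risk is a missed peri-procedural MI. The risk of procedural troponin release being counted as spontaneous MI is secondary and depends on further findings. Neither rate can be computed from the documents.

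The point concerns one descriptive secondary endpoint. The primary endpoint, 1-year all-cause mortality, and the sample size of 866 are untouched.

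**What to change.** 1. Reconcile Table 2 footnote a, Table 3 and section 6.2.4 with Appendix D, so that the scheduled sample falls in the interval to which the peri-procedural criterion applies. State the window in hours from the procedure, so that day counting no longer matters.
2. Record the hours from procedure to draw on the case report form.
3. State, in the protocol or the committee's charter, how a routine sample drawn after 72 h is adjudicated in two cases: when the event began within 72 h, and when there was no new clinical event.

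The cost is wording in three places, one time field and one adjudication rule. No blood draw is added. The adjudication rule can also be applied to patients already sampled, where the draw time can be recovered.
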